### 5.3 Statistical Methods

A total of 50 participants will be recruited for this study. Three radiologists will be recruited to conduct the reader study.

We will perform sensitivity, specificity and area under the curve (AUC) analysis of the imaging modalities based on radiologist reader studies. We will also perform reader confidence studies in evaluation of imaging characteristics relevant to wrist pain imaging.

The primary outcome of interest is the sensitivity of Tomo-E is defined as the ability of readers (radiologists) to detect wrist fractures in patients. This will be determined by performing a reader study with radiologists. Using these results, we can determine the mean confidence score of radiologist readers using the new device as compared to the competing modality. We will also test the primary null hypothesis that the difference between the two mean confidence scores is zero in the target population.

For the confidence study, the average confidence scores and the corresponding standard deviations will be reported. Furthermore, to test whether the mean confidence score is larger than zero, a linear mixed-effects model will be used to analyze data, where the outcome variable is the confidence scores collected in this study and only a grand mean parameter is in the independent list. Additionally, a random intercept is used in the model to account for the correlation among readers when reading the images from the same patient. The Wald's test based on model fit will be used to test whether the grand mean parameter is larger zero. When the p-value from this test is less than 0.05, it will be concluded that there exists significant evidence that readers have more confidence with the Tomo-E modality compared to the other modality. The estimated mean confidence score is given by the grand mean parameter and its 95% confidence interval will be reported. We anticipate that it would be meaningful to detect a mean confidence score of greater than 1 between the modalities.

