For the primary and secondary objective, we will estimate the sensitivity and specificity for a pre-specified cutoff of review scores to detect wrist fracture. Generalized estimating equation will be used to produce such estimates, where diagnosis outcomes from readers are treated as clustered data and a compound symmetry working covariance matrix is used. Normal distributions will be used to construct 95% confidence intervals. Bootstrap method may be used when the normality assumption is of concern. For the AUC analysis, the same estimating procedures will be used to obtain the sensitivity and specificity when varying cutoff scores then the AUC will be calculated using the trapezoidal rule. The confidence of the AUC will be obtained from bootstrap method.

For the confidence study, we expect no missing data or drop out. For any missed data during the reader study, we will question the reader to collect the data. The only primary hypothesis test is whether the mean confidence score is zero with a significance level of 0.05. There is no need to adjust multiple tests. All hypothesis tests that are observed to be not statistically significant will be reported as being inconclusive.

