#### **5.4 Sample Size and Power**

A typical sensitivity of radiographs for wrist fractures is approximately 65%[5] We estimate that our sensitivity using the Tomo-E system will be approximately 80%. Thus we will need 50 patients to detect this difference, assuming a prevalence of approximately 33% in our test population and with 3 readers, that we will have 70% power to detect differences between the two modalities.

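### The 95% intervals for sensitivity rest on normal quantiles and about 17 fracture patients, with no small-sample correction and no stated scale; on the proportion scale, which the plan permits, they cover about 89–92%

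*Combined protocol and SAP*

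**What the plan says.** Section 5.3 treats the readers' diagnoses as clustered data and estimates sensitivity and specificity by GEE with a compound symmetry working covariance. The interval rule is one sentence: "Normal distributions will be used to construct 95% confidence intervals". The fallback is another: "Bootstrap method may be used when the normality assumption is of concern". The section does not give the link function, the scale on which the interval is formed, the variance estimator, the bootstrap type, the unit resampled, or what would trigger the bootstrap.

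The sizes come from two places. Section 5.3: "A total of 50 participants will be recruited for this study" and "Three radiologists will be recruited to conduct the reader study". Section 5.4 adds the prevalence, "assuming a prevalence of approximately 33% in our test population", and expects sensitivities of about 65% for radiography and 80% for Tomo-E.

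**The concern.** Patients, not reads, are the independent units. Three reads of each of about 17 fracture patients do not make 51 independent observations, and the clustering in the plan recognises this. With so few clusters, three things shorten or misplace a normal interval:

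- The uncorrected robust variance is biased low.
- The normal quantile ignores the uncertainty in that variance.
- Near 80%, a symmetric interval on the proportion scale fits a skewed estimate badly.

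Section 5.3 says the only primary hypothesis test concerns the confidence score. No test of sensitivity is specified, so the primary endpoint will be judged largely through its interval. An interval labelled 95% that covers 90% misses the true value twice as often as the reader is told. If the scale and the bootstrap type are chosen after the data are seen, the choice can also move the limits.

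**Working it through.** **Plan's own figure.** The only coverage figure in the documents is the nominal 95%. The 70% power in Section 5.4 is a separate matter and is not used here.

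**Inputs.** From the plan: 50 patients, 3 readers, prevalence 33%, sensitivities 65% and 80%. Assumed: the cluster is the patient; reads within a patient are beta-binomial, with an ICC of 0.2–0.6 (0–0.8 in the wider check); specificity is 90%.

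**Clusters.** 50 × 0.33 = 16.5, so about 17 patients with a fracture and about 33 without.

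**Estimator.** With three reads per patient, the intercept-only exchangeable GEE estimate is the mean of the patient-level proportions. The uncorrected robust standard error is √(Σ(yᵢ − ȳ)²)/n.

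**Shortfall before any skewness.** The expected uncorrected variance is 16/17 = 0.941 of the true variance, so the effective multiplier is 1.960 × √0.941 = 1.901. The t quantile on 16 degrees of freedom is 2.120. Even if patient means were exactly normal, ±1.901 on t(16) covers about 92.5%. This matches the result at 65%. The further loss at 80% comes from skewness.

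**Coverage of nominal 95% intervals, 17 fracture patients.** Exact enumeration, ICC 0–0.8:

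| Interval | Sensitivity 65% | Sensitivity 80% |
|---|---|---|
| Normal, proportion scale | 92.0–92.6% | 88.2–91.1% |
| Normal, logit scale | 93.9–95.8% | 93.1–94.6% |
| Percentile bootstrap over patients | 92.2–93.1% | 88.2–91.7% |
| BCa bootstrap over patients | 93.1–96.1% | 92.3–94.5% |

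Simulation with ICC restricted to 0.2–0.6 gives 91.9–92.2% at 65% and 89.5–90.1% at 80% for the normal proportion-scale interval. Fitted GEE models at 80% and ICC 0.5 gave 87.7% with an identity link and 93.0% with a logit link. Letting the number of fracture patients vary as Binomial(50, 0.33) changes little: 89.1–91.7% on the proportion scale and 93.1–95.6% on the logit scale (ICC 0.2–0.8).

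**Specificity.** At an assumed 90% with 33 patients, the normal proportion-scale interval covers 88.5–89.6%.

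**Paired modality difference (65% against 80%).** Normal interval 89.6–92.3%; percentile bootstrap 90.5–92.3%. The patient-level t interval covers about 94–95% in most settings and 91.6% at the highest correlations tried.

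**After the change** (logit scale, Mancl-DeRouen variance, t quantile; ICC 0.2–0.6): 97.0–97.7% at 65%, 95.9–96.1% at 80%, and 94.4–96.0% for specificity.

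**What it does to one interval.** Take an estimate of 80% and ICC 0.4.

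- SE = √(0.8 × 0.2 × (1 + 2 × 0.4)/3/17) = 0.0751.
- Proportion scale: 0.80 ± 1.960 × 0.0751, or 65.3% to 94.7%.
- Logit scale: SE = 0.0751/0.16 = 0.470. Then 1.386 ± 1.960 × 0.470 back-transforms to 61.4% to 90.9%.
- Corrected: here the Mancl-DeRouen standard error is 17/16 = 1.0625 times the uncorrected one. Then 1.386 ± 2.120 × 1.0625 × 0.470 gives 58.1% to 92.0%.

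**The case against.** The strongest reply is that the plan never commits to the proportion scale. The outcome is binary, so a logit-link GEE with a normal interval on the linear predictor fits the sentence equally well, and that interval covers about 93–95%. This stands. A reader might infer that the planned intervals simply cover 89–92%, but the documents support that only for one permitted reading. Even on the logit scale, though, coverage is mostly a little short, and the scale is left open.

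A reader might also infer that the bootstrap fallback is no better. That is true of percentile limits only. BCa limits do largely repair the problem, and the plan names neither type.

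The uncorrected robust variance is likewise an inference: the plan states a working covariance, not a variance estimator. And Section 5.3 describes no interval for the modality difference, so the 90–92% shows what its normal rule would give if applied there. The difference still matters, because Section 2.1 makes the primary objective a comparison.

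Finally, this is a pilot study, and no decision rule is tied to these intervals. That limits the consequence but does not make a 95% label correct.

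**Conclusion.** The concern holds conditionally. With about 17 fracture patients, a plain reading of the interval rule, on the proportion scale and without correction, gives about 92% coverage at 65% sensitivity and 89–90% at 80%. The miss rate there is therefore 8–11% instead of 5%. Other choices the plan allows come much closer to nominal. The defect is a stated normal-quantile rule that is poor for this sample size, together with an unstated scale and bootstrap type that decide how poor it is.

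The figures rest on beta-binomial reads, an assumed ICC and an assumed 90% specificity. Across ICC 0–0.8 the proportion-scale result moves by less than 1 percentage point at 65% (92.0–92.6%) and by about 3 points at 80% (88.2–91.1%). The point does not invalidate the trial. It should be settled before the reader study is analysed.

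**What to change.** Replace the interval and bootstrap sentences in Section 5.3 with:

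> Intervals for sensitivity and specificity are built on the logit scale and back-transformed, using a bias-corrected robust variance (Mancl-DeRouen) clustered on patient and a t quantile with (patients in the denominator − 1) degrees of freedom. If all reads in a denominator agree, an exact (Clopper-Pearson) interval based on the number of patients is used. The modality difference in sensitivity is the mean of the patient-level differences in the proportion of positive reads, with a t interval on (fracture patients − 1) degrees of freedom, and likewise for specificity. Any bootstrap resamples patients and uses BCa, not percentile, limits.

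Specifying the scale is essential. On the proportion scale, t(16) with an n/(n − 1) variance correction still leaves 91.4–94.5% at 80% sensitivity. The exact-interval clause is needed because the logit interval is undefined when every read is correct. That is rare at 80% but reaches about 5% of samples at an assumed 90%. With 17 patients all positive, the exact lower limit would be 0.025^(1/17) = 80.5%.

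The cost is a few sentences, standard software and no new data. On the logit scale the corrected interval is (2.120/1.960) × (17/16) = 1.149 times as long as the normal one, about 15% wider. It is mildly conservative near 65% sensitivity, at about 97–98%.

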#### **2.2.3 Area Under the Curve (AUC) Comparison**

To compare the area under the curve (AUC) for Tomo-E compared to wrist radiography for fracture detection.

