#### **4.4 Reader Study**

Upon completion of all study image data collection, a reader study will be performed with three MSK fellowship trained radiologists. All images will be reconstructed with our fast-reconstruction algorithm and presented on 3MP viewing monitors with PACS viewing software with conventional zoom/pan/window and level tools. The readers will not be blinded whether the images are from Tomo-E.

Each radiologist will be randomly presented with either the patient's diagnostic radiographs or tomosynthesis study in a random order. They will be asked to review the scan for the presence of a fracture, and comment on location (specific bone) and fracture type. They will be asked their confidence rating on a scale of 0 to 100%.

A washout period of four weeks will be utilized so that the radiologists will have "forgotten" their initial interpretations. At this timepoint, the other modality for each patient will be randomly presented. Diagnostic accuracy will be defined by the presence of a fracture as defined by the clinical diagnosis by the attending orthopedic surgeon at 2 months post imaging during the patients' routine clinical care, such as cast placement, surgery, or follow-up imaging. Sensitivity and specificity to the presence of fractures will be estimated and evaluated between the modalities.

The order that imaging modalities will be presented will be randomly assigned using a computational software in collaboration with the study biostatistician. This randomization schedule will be created prior to the beginning of the reader study and will not be shared with any of the readers.

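### The AUC is built from readings pooled over readers at common cutoffs, which can distort the modality difference in either direction; separately, no paired AUC difference or interval for it is specified

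*Combined protocol and SAP*

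**What the plan says.** Section 2.2.3 makes the AUC a comparison: "To compare the area under the curve (AUC) for Tomo-E compared to wrist radiography for fracture detection".

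Section 5.3 (Statistical Methods) builds the AUC from the same machinery as the sensitivity and specificity estimates. In that GEE, "diagnosis outcomes from readers are treated as clustered data and a compound symmetry working covariance matrix is used". For the AUC, the GEE is re-run to give sensitivity and specificity "when varying cutoff scores then the AUC will be calculated using the trapezoidal rule". On uncertainty it says only: "The confidence of the AUC will be obtained from bootstrap method". It mentions no reader-specific ROC curve, averaging over readers, AUC difference or unit of resampling.

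The design is fully paired. Section 5.3 states: "Three radiologists will be recruited to conduct the reader study". Section 4.4 (Reader Study) has each of them read one modality per patient and, after a four-week washout, the other: "At this timepoint, the other modality for each patient will be randomly presented".

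The 0-100 score is described in two ways. The list in Section 4.5 makes it confidence in the interpretation; the form in Appendix A makes it confidence that a fracture is present.

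**The concern.** There are two separate faults.

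First, an ROC curve built from pooled readings at common cutoffs assumes that a score of, say, 60 means the same to every reader. A free 0-100 rating without described anchors or calibration does not ensure this. Differences between readers in where they place their scores then enter the curve as if they were diagnostic performance. Because the objective is a comparison, what matters most is whether this shifts the difference between modalities, and it can do so when scale use differs between Tomo-E and radiography. From the pooled result alone, the sponsor could not tell whether a gain had been shrunk or exaggerated.

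Second, the plan has a comparison as its objective and paired reads in its design, but defines no paired contrast. An interval for each AUC on its own would not use the pairing and would not directly answer Section 2.2.3.

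**Working it through.** **Inputs from the documents.** Three readers; every reader scores every patient in both modalities; a reader-clustered GEE at each cutoff; the trapezoidal rule. The plan gives no AUC figure to reproduce: the only power statement (Section 5.4) concerns sensitivity.

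**Assumed, not in the documents.** True AUC 0.86 for Tomo-E and 0.80 for radiography, the same for each reader; normally distributed scores; reader offsets drawn from N(0, s²), with s in units of the within-reader score SD.

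**Step 1: what the described estimator is.** With an exchangeable working correlation, equal cluster sizes and no reader term, the GEE estimate at any cutoff is the raw proportion over all readers' readings. The trapezoid over those proportions is therefore the Mann-Whitney AUC of the pooled readings. In a test dataset both gave 0.7582, while the average of the three readers' own AUCs was 0.872.

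**Step 2: size for readers of equal ability.** The pooled AUC is the mean over the nine ordered reader pairs (i, j) of Φ((d + oᵢ − oⱼ)/√2), with d = √2·Φ⁻¹(A). Three pairs have i = j and return A. In the other six, oᵢ − oⱼ ~ N(0, 2s²). Hence

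expected pooled AUC = A/3 + (2/3)·Φ(Φ⁻¹(A)/√(1 + s²)).

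- A = 0.86, s = 1.0: 1.0803/1.4142 = 0.7639, Φ = 0.7775, so 0.2867 + 0.5184 ≈ 0.805.
- A = 0.80, s = 0.3: 0.8416/1.0440 = 0.8061, Φ = 0.7899, so 0.2667 + 0.5266 = 0.7933.
- Difference: 0.8050 − 0.7933 = 0.0117, or 0.012 against a true 0.060.

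| s | Tomo-E pooled (true 0.86) | Radiograph pooled (true 0.80) | Difference, same s in both | Difference, Tomo-E s, radiograph 0.3 | Difference, radiograph s, Tomo-E 0.3 |
|---|---|---|---|---|---|
| 0.3 | 0.853 | 0.793 | 0.060 | 0.060 | 0.060 |
| 0.5 | 0.842 | 0.783 | 0.059 | 0.049 | 0.070 |
| 0.75 | 0.824 | 0.766 | 0.058 | 0.031 | 0.087 |
| 1.0 | 0.805 | 0.749 | 0.056 | 0.012 | 0.104 |

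Each pooled AUC falls as s grows. The difference barely moves when s is equal, shrinks when Tomo-E has the wider offsets, and grows when radiography has them.

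**Step 3: readers of unequal ability.** Take separations of 1.8, 1.8 and 0.6 within-reader SDs, with the third reader's scores compressed to one fifth of the spread around mid-scale. The reader AUCs are 0.898, 0.898 and 0.664, averaging 0.820. Of the nine pairs, four give 0.8985, four cross pairs with the third reader give Φ((0.9 + 0.06)/√(1 + 0.04)) = 0.8267, and one gives 0.6643. Pooled: (4 × 0.8985 + 4 × 0.8267 + 0.6643)/9 = 0.841. Pooling here raises the AUC above the reader average.

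**Step 4: the missing paired difference.** Section 5.4's sensitivities of 65% and 80%, with an assumed specificity of 80%, imply AUCs of 0.807 and 0.883. A simulation used 17 fracture and 33 non-fracture patients (33% of 50 is 16.5), three readers, assumed case correlations, a patient-level bootstrap and 400 runs.

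- No reader offsets: the interval for the paired difference lay above zero in 36% of runs; two separate AUC intervals were disjoint in 2%. Pooling plays no part in this gap.
- Offsets of −0.5, 0, +0.5 for radiography and −1, 0, +1 for Tomo-E: the paired interval lay above zero in 10% of runs with the pooled AUC and 37% with the reader-averaged AUC.
- The two offset patterns exchanged: 78% pooled, 36% reader-averaged.

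**The case against.** A reader might infer that the pooled AUC is always too low, and that the plan will therefore hide a real Tomo-E advantage. The documents do not support that. Step 3 shows pooling can raise the AUC. Similar scale use in both modalities almost cancels in the difference, and wider variation under radiography would flatter Tomo-E. Nothing in the protocol says that scale use varies more on Tomo-E. The readers are three fellowship-trained musculoskeletal radiologists from one institution using one form, which argues for modest offsets. Tomo-E is a new device and no reader training on it is described, so unequal scale use is plausible, but that is conjecture.

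A reader might also infer that Section 5.3 prescribes separate intervals for the two AUCs. It does not: it leaves open what is bootstrapped, so the fault is under-specification rather than a stated wrong method.

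Finally, this is a pilot, the AUC is a secondary objective, and no AUC hypothesis test is planned. That limits the weight of the point but does not remove it: the comparison in Section 2.2.3 still has no defined estimate of the difference.

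**Conclusion.** The concern holds in limited form. The AUC described in Section 5.3 pools readers at common cutoffs. For readers of equal ability who use the scale differently this lowers the AUC; for readers of unequal ability it can raise it. The modality difference can be distorted either way, mainly when scale use differs between modalities: under the assumptions above, a true 0.060 could appear as anything from 0.012 to 0.104, but as 0.056 to 0.060 if scale use is alike. These sizes rest on assumed AUCs and offsets that the documents neither give nor exclude.

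The absence of a paired difference, its interval and a resampling unit needs no such assumptions; it follows from the text. It weakens precision and inference and is not itself a source of bias in the AUC. Both faults concern a secondary objective and should be corrected before the reader study is analysed.

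**What to change.** Replace the AUC wording in Section 5.3 along these lines:

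- Compute the empirical AUC separately for each reader and modality, and average over the three readers within modality. Offsets between readers then have no effect.
- Take as the estimate the reader-averaged Tomo-E AUC minus the reader-averaged radiograph AUC.
- Obtain its 95% confidence interval by bootstrapping patients, keeping all six reads of a patient (three readers, two modalities) together.
- Name the score as confidence that a fracture is present, as on the Appendix A form, and reconcile Section 4.5 with it. Confidence in the interpretation does not order cases from non-fracture to fracture and cannot serve as an ROC score.

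The cost is a change of wording. It uses data already to be collected, adds no patients or reads, and is simpler than a GEE at every cutoff. The one drawback is that a patient-only bootstrap treats the three readers as fixed, so the interval does not extend to other radiologists. The plan should say so.

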### **2.1 Primary Objective**

The primary objective is to compare (using a reader study) the sensitivity of Tomo-E compared to radiography of the wrist in detecting wrist fractures.

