#### **2.2.2 Reader Confidence**

To compare radiologist confidence of Tomo-E compared to wrist radiography for the evaluation of:

- Articular surfaces
- Cortical surface of the bones
- Joint spaces
- Soft tissue structures
- Subarticular structures

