#### **4.5 Variables of Interest**

Primary Variables of Interest:

- Presence of fracture based on imaging (T/F)
- Confidence in interpretation of image set (0 to 100%)

Secondary Variables of Interest

- Reader confidence in articular surface evaluation (1-5)
- Reader confidence in Cortical surface evaluation (1-5)
- Reader confidence in Joint Space evaluation (1-5)

- Reader confidence in Soft tissue Structures evaluation (1-5)
- Reader confidence in Subarticular structure evaluation (1-5)

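### The objective, endpoint and sample size concern sensitivity, but the only primary hypothesis test is on reader confidence, and no contrast, interval or test is specified for the two sensitivities

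*Combined protocol and SAP*

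**What the plan says.** Section 2.1 is explicit: "The primary objective is to compare (using a reader study) the sensitivity of Tomo-E compared to radiography of the wrist in detecting wrist fractures". Section 5.1 names sensitivity as the primary endpoint, 5.3 names it again as the main outcome, and 5.4 bases the 50 patients and 70% power on sensitivities of 65% for radiographs and 80% for Tomo-E.

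The hypothesis test is placed elsewhere. Section 5.3 says "We will also test the primary null hypothesis that the difference between the two mean confidence scores is zero in the target population", and the synopsis (Statistical And Analytic Plan) repeats the sentence. Section 5.3 later adds "The only primary hypothesis test is whether the mean confidence score is zero with a significance level of 0.05" and concludes that multiplicity needs no adjustment.

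For sensitivity and specificity, 5.3 plans GEE estimates at a score cutoff, with normal-theory 95% intervals and the bootstrap as a fallback. The nearest text to a comparison is in 4.4: "Sensitivity and specificity to the presence of fractures will be estimated and evaluated between the modalities". No method is attached to it.

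Reader confidence is a secondary objective in 2.2.2: "To compare radiologist confidence of Tomo-E compared to wrist radiography for the evaluation of" five anatomical structures, which 4.5 rates from 1 to 5. Section 4.5 also lists an overall 0 to 100% confidence rating among the primary variables of interest.

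**The concern.** A significant result on the declared primary test licenses this conclusion in 5.3: "it will be concluded that there exists significant evidence that readers have more confidence with the Tomo-E modality compared to the other modality". That does not answer objective 2.1. Readers know which modality they are viewing (4.4), and confidence can rise with no gain in detection.

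The objective that matters has no decision rule. Several analyses would fit the present wording: the yes/no call or a score cutoff, paired or unpaired, with or without a small-sample correction. They can disagree, and choosing among them after the reads are known would be post hoc.

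The declared test is itself incomplete. Section 5.3 does not say whether the overall 0 to 100% score or the 1 to 5 ratings are tested. It states a null of zero difference but describes the model as a way "to test whether the mean confidence score is larger than zero", so sidedness is unclear.

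**Working it through.** **1. Place of each quantity in the plan**

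| Element | Sensitivity | Reader confidence |
|---|---|---|
| Objective | Primary (2.1) | Secondary (2.2.2) |
| Endpoint | Primary (5.1) | Not listed in 5.1 or 5.2 |
| Variable of interest | Fracture yes/no, primary (4.5) | Overall score primary, five ratings secondary (4.5) |
| Sample size | Basis of 5.4 | None |
| Hypothesis test and alpha | None | Sole primary test, 0.05 (5.3, synopsis) |
| Modality contrast | None specified | Difference in means (5.3) |

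**2. The plan's own 70%**

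Inputs from 5.4: sensitivities 0.65 and 0.80, 50 patients, prevalence 0.33, three readers. Fracture patients = 50 × 0.33 = 16.5, so there are 3 × 16.5 = 49.5 fracture reads per modality. Section 5.4 gives no alpha, sidedness, test or correlation. Alpha 0.05 is assumed.

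- Two-proportion test, reads treated as unpaired and independent, pooled variance: power 38.5% two-sided and 51.1% one-sided. Power of 70% would need 109 or 83 fracture reads per modality.
- Paired McNemar approximation with independent readers: 70% needs a between-modality correlation of about 0.59 two-sided or 0.44 one-sided.
- One-sided exact one-sample test against a fixed 65%: 71.1% with 50 reads, 68.5% with 51. This is near 70% but does not compare two modalities.

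The 70% can therefore be neither confirmed nor refuted, because the test behind it is not stated.

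**3. A paired test of the sensitivities (two-sided 0.05)**

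Let r be the between-modality correlation and ICC the between-reader correlation of the paired differences. Both are assumed.

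Var(d) = 0.65×0.35 + 0.80×0.20 − 2r√(0.65×0.35×0.80×0.20) = 0.3875 − 0.3816r

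SE = √[Var(d)(1 + 2·ICC)/49.5]

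| r | ICC | SE | Power, normal | Power, t (15.5 df) |
|---|---|---|---|---|
| 0 | 0.3 | 0.112 | 27% | 24% |
| 0 | 0 | 0.0885 | 40% | 36% |
| 0.3 | 0.1 | 0.081 | 45% | 41% |
| 0.6 | 0.3 | 0.072 | 55% | 50% |
| 0.6 | 0 | 0.0566 | 76% | 70% |

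The largest r that margins of 0.65 and 0.80 allow is √[0.65×0.20/(0.35×0.80)] = 0.68. The 95% half-width with the t reference runs from 2.13 × 0.0566 = 0.12 to 2.13 × 0.112 = 0.24.

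**4. Need for a small-sample correction**

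A simulation set both sensitivities at 70%, with latent normal reads, fracture patients drawn from Binomial(50, 0.33), three readers, six correlation settings and 6,000 runs each. Type I error was 7.0–8.1% with the uncorrected robust z and 4.3–5.5% with the t reference. A repeat under other correlation settings gave about 7.2–8.1% and 4.6–5.4%.

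**5. How readily the confidence test can reject**

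This is an illustration with every input assumed: the 0–100 score, a 5-point shift, SD of paired differences 15, 20 or 25, between-reader correlation 0.3, and 150 paired reads.

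SE = SD × √[(1 + 2×0.3)/150] = 1.55, 2.07, 2.58

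- One-sided 0.05: rejection 94%, 78%, 61%.
- Two-sided 0.05: rejection 90%, 68%, 49%.

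These rates do not involve the sensitivities. If the same score is also cut to define a positive read, however, a shift in it could move the estimated sensitivity too.

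**The case against.** The strongest reply is that the sentence about the sole primary test sits in a paragraph that opens by referring to the confidence study, so it may be limited to that part. The same section assigns GEE estimates with intervals to the primary objective, 4.4 shows that a comparison is intended, and the synopsis calls this a pilot, where estimation alone can be a legitimate aim.

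The limited reading fails. The synopsis and the earlier text of 5.3 both call the confidence null primary without any such limit. The intention to compare is real, but it has no method, and separate intervals for two sensitivities measured in the same patients are not a paired comparison. An estimation-only pilot would be coherent, but it would not claim 70% power to detect a difference, and it would still need an interval for that difference.

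Some points about the figures stand. Only a 5-point shift is shown above. The one benchmark in 5.3 is a mean score above 1, on an unstated scale. A 1-point shift on 0–100 with the same standard errors would be detected only about 10–16% of the time one-sided and 7–10% two-sided. If the 1 to 5 ratings are what is tested, the illustration does not apply. One-sided with a normal reference, the extreme rows of the sensitivity table give 38% and 84%. None of this alters the mismatch between objective and test.

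**Conclusion.** The concern holds, and it must be fixed before the reads are analysed. The core finding comes from the text alone and rests on no assumed figure: the primary objective has no specified contrast or decision rule, and the only primary test addresses a different quantity, whose success would not establish better fracture detection.

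The size of the problem depends on correlations that the plan does not give. Over r from 0 to 0.6 and ICC from 0 to 0.3, two-sided power for the planned 15-point difference is 24–70% (t) or 27–76% (normal), and the interval half-width is 12–24 points. With the t reference, 70% is reached only with r near 0.6 and independent readers.

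**What to change.** In 5.3 and the synopsis:

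- State the primary null hypothesis as equal sensitivity of Tomo-E and radiography, tested at two-sided 0.05.
- Fit one GEE to the reads of reference-positive patients, both modalities together, with a modality term and the patient as cluster. Report the paired difference with a two-sided 95% interval and a small-sample correction, since only 16 to 17 fracture patients are expected.
- State before reading starts whether the yes/no fracture call (4.4, 4.5, Appendix A) or the score cutoff (5.3) defines a positive read.
- Make the confidence test secondary, and name its score and sidedness.
- Report specificity and AUC differences as secondary in the same paired way, with a patient-level bootstrap for AUC.
- Replace the sentences on the sole primary test and on multiplicity with: *The single primary hypothesis test is the sensitivity difference. Specificity, AUC and confidence comparisons are secondary, reported with 95% CIs and without a confirmatory claim, so no multiplicity adjustment is made.*

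In 5.4, restate the power for this paired test with its assumed between-modality and between-reader correlations.

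The cost is text changes and one power recalculation, with no new patients or reads. The downside is a low-powered primary test that may be inconclusive. Two limits remain: the fracture calls are made unblinded to modality, so that bias is not removed, and clustering by patient alone leaves out variation between readers, so the result applies to these three readers.
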